9.1.2. Epworth Sleepiness Scale (ESS)

The ESS measures EDS in 8 different situations with four choices of responses from 0 to 3. ESS total score ranges from 0 to 24.

The ESS questionnaire will be completed by the participants at the baseline visit and at the End of Treatment (ET) visit.

ESS scores will be summarized for the baseline, ET, and the mean change from baseline at ET for all participants. Summarized statistics will include number of participants, mean, standard deviation, median, minimum, and maximum. Mean (\pm SD) ESS scores will be plotted over time.

A listing of all ESS data will be presented.

9.1.3. Participant Global Impression of Change (PGIc)

PGIc measures participant's impression of improvement in the sleepiness from previous visit. There are 7 categories ranging from very much improved to very much worse with 3 categories for improvement, 3 categories for no improvement, and one category for no change.

PGIc data will be collected at the end of the treatment period or at Early Discontinuation. A summary statistics report will include the number of participants, tabulation of each of the 7 categories and percent. The number and percent of participants reported improved and worsen will be generated.

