Adverse Events and Serious Adverse Events Reporting (Appendix 7)	X	X	X	X	X	X	X
Concomitant Medications	X	X	X	X	X	X	X
Food and Drug Dosing Diary (Appendix 4)	X ⁵	X	X	X	X	X	X
Assess diary for completeness and compliance after start of dosing							

Procedure	Screening Period (Up to 30 days before Day 1)	Baseline Period	Intervention Period (Open Label Conversion and Treatment Optimization Period)		Discontinuation (E/D) ³	Safety Follow-up Period
			Conversion from Xyrem to XYWAV ¹	Treatment Optimization on XYWAV ²		
Visit (V) Number ⁴	V1	V2	V3	V4 Clinic Visit	V5, V6 Phone Call	V7 Clinic Visit
Visit Window +/- Day or End of Week (W)	Day -30 to -1	Day 1	Day 15 + 1 day	W3 +3 days	W4, W5 +3 days	W6 +3 days
Dispense study drug			X		X	
Collect study drug, measure compliance					X	X

Abbreviations: BP = blood pressure; EDS = excessive daytime sleepiness; HR = heart rate; RR = respiratory rate; TSH = thyroid-stimulating hormone; UA = urinalysis

1. All participants will begin XYWAV treatment at the beginning of the Intervention (Open-label Conversion and Treatment Optimization) period, starting the night of Visit 3/Day 15 and continue through to the End of Treatment (ET) (Visit 8) or Early Discontinuation (E/D), as applicable.
2. Participants must be on an optimized dose of XYWAV for at least the final 2 weeks of the Intervention Period.
3. Following ET (Visit 8) or E/D, investigators will determine the appropriate course of care with the participant, with the option to resume medications that were discontinued prior to or during study participation.
4. The investigator may have the participant attend an unscheduled visit at any time during the study, if deemed necessary.
5. The participant is expected to start indicated diary completion on the morning after the participant enters the Baseline period (Day 1).
6. NVAS will be captured daily during the last 7 days of the Baseline (Xyrem-stable dose and regimen) period and the last 7 days of the Intervention period (on XYWAV) prior to the ET visit, or prior to the E/D visit, if possible.

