This current study (JZP258-401) is a multi-center, open-label, single-arm, phase 4 trial that seeks to build upon the demonstrated benefits of XYWAV and provide further descriptive evidence of safety, effectiveness, tolerability and treatment optimization in participants switching from Xyrem to XYWAV. The study will include comparative assessments related to treatment-based and exposure-related adverse events (AE), tolerability, and therapeutic effectiveness of disease control between Xyrem and XYWAV. Participants will be switched from Xyrem to XYWAV at the same dose and regimen as Xyrem. Once the investigator determines that a stable dose and regimen of XYWAV is achieved, participants will be allowed to dose with or without food. If needed, XYWAV will be titrated to an optimized dose and regimen based on efficacy and tolerability, under the advisement and instruction from the investigator.

Success in this study will be indicated by seamless switching of the majority of participants from Xyrem to XYWAV, with little or no changes in dose strength or regimen. Additionally, evidence will be provided to support participant preference for XYWAV based on its lower level of sodium, potentially improved tolerability profile, a safety profile typical of oxybate, and similar disease control as participant's current Xyrem dose and regimen. Collectively, these data are expected to expand the knowledgebase of clinical experience in the population of participants with narcolepsy transitioning from Xyrem to XYWAV.

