8.2.3. Participant Global Impression of Change (PGIC)

The PGIC is a 7-point Likert-type rating based on a 7-point scale ranging from 1 (very much improved) to 7 (very much worse) that is widely used to assess efficacy in clinical drug trials ([Schmitt 2014](#); [Bogart 2017](#)). The PGIC assessment will be administered in electronic format to participants at the ET or E/D visits, as indicated in the SoA (Section 1.3), with appropriate training, instructions and supervision provided for completing the assessment, as needed.

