9.4.2. Effectiveness Endpoints

Effectiveness endpoints will be summarized descriptively. The following effectiveness endpoints will be assessed in this study:

- Change in weekly rate of cataplexy attacks: Participants will be required to complete an electronic Cataplexy Frequency Diary ([Appendix 5](#)) daily. Based on these data, the weekly rate of cataplexy attacks (for NT1) will be established. Additionally the change in weekly cataplexy rate from the last week of the Baseline period (on Xyrem) to that of individual weeks during the Open Label Conversion and Treatment Optimization Period will be summarized. For participants experiencing at least 1 day of cataplexy attack, the weekly number of cataplexy attacks will be derived as the average number of daily attacks from days with non-missing data within the week, multiplied by 7.
- Change in Epworth Sleepiness Scale (to assess EDS): Changes in ESS scores between the Baseline period and ET or E/D, as applicable, will be summarized.
- Participant Global Impression of Change: PGIC values will be measured at the ET or E/D, as applicable, in accordance with the SoA ([Section 1.3](#)). The number of participants with each response will be summarized. Additional categorization of the scores may be performed and summarized.
- Time to optimized dose and regimen is defined as the time from the first dose and regimen to the optimized dose and regimen of XYWAV, where the optimized dose and regimen indicates the final dose and regimen that remains unchanged throughout the remainder of the Intervention (Open-label Conversion and Treatment Optimization) period. Compliance is not considered in the derivation of the time to achieve optimized dose and regimen. The time to achieve optimized dose and regimen will be summarized.
- Additionally, the number of changes from the first dose and regimen to optimized dose and regimen, the number of participants dosing fasted versus dosing without consideration of food, and the timing and characterization of meals with regard to dosing of XYWAV ([Appendix 4](#)) will be summarized descriptively.

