6. ANALYSIS SETS

For purposes of analysis, the following populations are defined:

Table 1Analysis Set

Analysis Set	Description
All Screened	The All Screened Analysis Set will include all subjects who provided a signed informed consent for this study.
	This analysis set will be used to summarize the number of screened, screen failure and enrolled subjects.
Enrolled	All participants who sign the informed consent form and meeting all eligibility criteria for the study.
	This analysis set will be used to summarize participant disposition, major protocol deviations (as classified in CTMS), and inclusion/exclusion from the Safety Analysis Set, including reasons for exclusion from it.
Safety	The Safety Analysis Set will include all participants in the Enrolled Analysis set who take at least one dose of Xyrem after providing informed consent.
	This analysis set will be used for summaries of all endpoints, except those which only pertain to data captured during the Intervention Period.

Analysis Set	Description
XYWAV Safety	The XYWAV Safety Analysis Set will include all participants in the Safety Analysis Set who take at least one dose of XYWAV.
	This analysis set will be used for summaries of all endpoints which pertain to only data captured during the Intervention Period.
XYWAV Efficacy	The XYWAV Efficacy Analysis Set will include all participants in the XYWAV Safety Analysis Set who finish the course of study.
	This analysis set will be used for summaries of all endpoints which pertain to only data captured during the Intervention Period.

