7.2.3. Visit Windows

Except where specified, all data will be summarized using the CRF visit at which the data was collected. Where data is captured at an Early Termination visit, those data will be summarized with the regular visit at which the assessment would have been captured, relative to the study period during which the participant withdrew. For example:

- If a participant early discontinues during the Baseline Period, i.e. prior to the first dose of XYWAV, then data should be mapped to Visit 3.
- If a participant early discontinues during the Intervention Period, i.e. after at least one dose of XYWAV, then data should be mapped to the next scheduled visit at which those data would have been captured, based on the Schedule of Assessments.

For data captured independent of a CRF visit, eg, Adverse Events, Concomitant Medications and Cataplexy Diary, the following rules will apply:

- If the reported date is on or prior to first dose of XYWAV then the data will be considered to be included into the Xyrem Baseline Period for summaries
- If the reported date is after the first dose of XYWAV while on or prior to the completion of treatment or early discontinuation, then the data will be considered to be included into the XYWAV Intervention Period for summaries.

Unscheduled visits in general will not be mapped (excluded from analyses) when the corresponding scheduled visit is present. Unscheduled visits will only be mapped when the scheduled visit is missing. If more than 1 unscheduled assessments are available, choose the one with the assessment date closer to the target study day specified below, if 2 assessments are equally close to the target day (but on different sides), the latter assessment will be chosen. In addition, unscheduled visits with the assessment date earlier than the date of first dose of XYWAV, or participants early discontinue the study prior to the first dose of XYWAV, the data can only be mapped up to Visit 3. If the assessment date is later than the date of first dose of XYWAV, the unscheduled data should not be mapped to any visit prior to Visit 3.

Study Period	Study Visit	Target Study Day
Baseline	Visit 2	1
Intervention	Visit 3	15

Intervention	Visit 4	22
Intervention	Visit 5	29
Intervention	Visit 6	36
Intervention	Visit 7	43
Intervention	Visit 8	57

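### SAP 9.1.3 describes the single end-of-treatment PGIc as change since the previous visit, which for a completer falls entirely on XYWAV; its reference period and domain must be checked against the item and stated

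*SAP*

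**What the plan says.** SAP 9.1.3 describes PGIc as the participant's "impression of improvement in the sleepiness from previous visit". The same section fixes the timing: "PGIc data will be collected at the end of the treatment period or at Early Discontinuation". Protocol 8.2.3 agrees ("The PGIC assessment will be administered in electronic format to participants at the ET or E/D visits"), as does Protocol 9.4.2 ("PGIC values will be measured at the ET or E/D, as applicable"). Neither protocol section names a comparator or recall period, and neither limits the rating to sleepiness. The PGIc item is not reproduced in any appendix.

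PGIc is a key endpoint under an objective to describe the switch from Xyrem to XYWAV (SAP 4.1.1 and 4.2.1). Protocol 2 says the study will include comparative assessments of "therapeutic effectiveness of disease control between Xyrem and XYWAV". SAP 9.1 summarises effectiveness in two sets. One is the XYWAV Safety Set. The other is the XYWAV Efficacy Set, defined in SAP 6 as "all participants in the XYWAV Safety Analysis Set who finish the course of study". SAP 7.6 lists the changes from the protocol and does not mention PGIc.

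On the Nausea Visual Analog Scale (NVAS), Protocol 9.4.4 and SAP 7.2.4 both average the available daily scores in the week and multiply by 7. Protocol 9.4.4 then says that the mean of each 7-day period is summarised. SAP 10.8 adds a 95% CI for the mean change.

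**The concern.** A change rating has no baseline measurement of its own; its comparator is whatever the question tells the participant to think back to. The general baseline rule in SAP 7.2.1 therefore cannot supply one. Since PGIc is asked only once, the previous visit cannot mean a previous PGIc assessment. It has to mean the preceding study visit, and for a completer that visit is already on XYWAV.

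Read this way, the improved and worsened percentages describe the last weeks on XYWAV and not the switch. SAP 9.1.7 makes the risk concrete by summarising PGIc for those who achieved an optimized dose. Under SAP 9.1.4, a completer in that group is on an unchanged dose and regimen from Visit 7 to Visit 8. A no-change answer would then say nothing about Xyrem, yet it could be taken as evidence that disease control was maintained after switching. SAP 5.5 allows interim data to be presented externally, so a misreading could spread before the final report.

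**Working it through.** **Inputs.** SAP 7.2.3 target days: Visit 3 = 15, Visit 4 = 22, Visit 5 = 29, Visit 6 = 36, Visit 7 = 43, Visit 8 = 57. SAP 7.2.2: first XYWAV dose on the night of Visit 3/Day 15; end of treatment is Visit 8. Protocol 1.3: 3-day windows at Visits 7 and 8.

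**Reproducing the plan's days.** Protocol 1.3 places Visit 7 at the end of week 6 and Visit 8 at the end of week 8. With target day = 7 × week + 1, week 6 gives 43 and week 8 gives 57, as in the SAP.

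**Completers, at target days.**
- Interval rated: 57 − 43 = 14 days.
- Start of the interval after the switch: 43 − 15 = 28 days.
- Xyrem days in the interval: 0.
- An interval starting at the conversion visit would be 57 − 15 = 42 days.

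**Completers, with visit windows.** The row label in Protocol 1.3 reads plus or minus, while the entries read plus 3 days, and the table is broken in the text available. Both readings are therefore shown.
- One-sided: shortest 57 − 46 = 11 days; longest 60 − 43 = 17 days.
- Two-sided: shortest 54 − 46 = 8 days; longest 60 − 40 = 20 days.
- Least favourable case: first dose 3 days late (Day 18) and Visit 7 three days early (Day 40). Visit 7 is then XYWAV Study Day 40 − 18 + 1 = 23, so the interval still contains no Xyrem time.

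**Early exits (XYWAV Safety Set).** Under SAP 7.2.3, for an exit after the first XYWAV dose, "data should be mapped to the next scheduled visit at which those data would have been captured"; for PGIc that is Visit 8. Ratings with different previous visits therefore share one row. The possible scheduled references are Visits 3, 4, 5, 6 and 7, which is 5, or 3 if the phone contacts at Visits 5 and 6 are not counted as visits. Only an exit before Visit 4 refers back to Visit 3 and so to Xyrem: within 22 − 15 = 7 days of the switch, or 25 − 15 = 10 days if Visit 4 is 3 days late.

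**Completers can also differ (both sets).** Protocol 1.3, note 4, says: "The investigator may have the participant attend an unscheduled visit at any time during the study". An unscheduled visit between Visits 7 and 8, if counted, shortens the interval. SAP 6 does not say that a missed Visit 7 removes a participant from the Efficacy Set. If one were missed, the interval would run from Visit 6 (57 − 36 = 21 days), or from Visit 4 if phone contacts are not counted (57 − 22 = 35 days). Each of these starts after the switch.

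**NVAS.** Let m be the mean daily score or mean change, with standard error s. The reported value is 7m with standard error 7s. The ratio 7m/7s = m/s, so direction and mean/SE do not change. Removing the factor makes the mean, the change and both CI limits one seventh as large and returns them to the instrument's scale. For cataplexy the same factor is meaningful, because a mean daily count times 7 is a weekly count.

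**The case against.** The best reply is that the SAP sentence is background, not a derivation. The operative rules are when to collect PGIc, to tabulate seven categories, and to count improved and worsened; none of these changes with the reference period. What participants rated was fixed by the electronic questionnaire. The objective is descriptive, Protocol 2 does not assign the Xyrem comparison to PGIc in particular, and ESS, the cataplexy diary and NVAS each have a Xyrem baseline.

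Much of this stands, and it keeps the impact small. It also rules out a stronger reading that a reader might infer: that the collected PGIc data fail to describe the switch. The documents do not show that, because the item is not in them. Nor does the SAP contradict the protocol on the reference point, since the protocol gives none. What remains is that the only reference period stated anywhere does not fit the objective. The reference period decides what the percentages may be said to show, even though the counts stay the same.

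A reader might also infer that mixed references affect only the XYWAV Safety Set, or that the completers' table cures the problem. Neither holds. Unscheduled or missed visits can vary the reference among completers too. Restricting to completers conditions on finishing, drops those who left early, and still provides no Xyrem reference.

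On NVAS, it is fair to say that the protocol and SAP agree on the factor of 7 and that it is a constant rescaling. It remains worth removing, because it takes a visual-analogue result off its scale and sits awkwardly with the protocol's statement that the 7-day mean is summarised.

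**Conclusion.** The point holds as a defect in the SAP's description of a key endpoint. Read as written, a completer's PGIc covers about 14 days, all on XYWAV; the range is 11 to 17 days with one-sided windows and 8 to 20 with two-sided windows. The absence of Xyrem time does not depend on which window reading is right. The sentence also narrows a global rating to sleepiness, and SAP 7.6 does not record this.

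The conclusion assumes that the previous visit means the preceding study visit. Whether the fault lies in the SAP wording or in the item cannot be settled from the documents. The number of participants with a different reference is unknown, because no dropout rate is given. The impact is limited to interpretation of PGIc in a descriptive study, but the correction is worth making because it costs almost nothing. The NVAS item is minor: a factor of exactly 7 in the reported values, with no effect on direction or mean/SE.

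**What to change.** - **PGIc definition.** Check the administered PGIc item. Replace the sentence in SAP 9.1.3 with the reference period and symptom domain that the item actually uses, presuming neither. Record any narrowing to sleepiness in SAP 7.6.
- **If the item did refer to the previous visit.** Say so in the labels of the PGIc tables for both analysis sets, and do not report PGIc as a Xyrem-versus-XYWAV result. Do not prefer the completers-only table.
- **NVAS (minor).** Delete the multiplication by 7 in SAP 7.2.4 and report the 7-day mean daily score on the instrument's scale. Record in SAP 7.6 that this departs from Protocol 9.4.4.

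The cost is one check of the questionnaire text, wording in SAP 9.1.3, 7.2.4 and 7.6, and table labels if needed. No new data, table or analysis is required.

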9.1.4. Dose and Regimen Changes in Intervention Period

Time to optimize dose and regimen is defined as the time (unit is day) from the first dose and regimen of XYWAV to the optimized dose and regimen of XYWAV, where the optimized dose and regimen is the final dose and regimen that remains unchanged throughout the remainder of the intervention period. Optimized dose and regimen is defined as follows:

- The final dose and regimen that a participant takes before or at Visit 7 that remains unchanged to Visit 8 when the participant completes the XYWAV treatment, regardless of the time between Visits 7 and 8.
- The final dose and regimen that remains the same for at least 2 weeks (14 days) for a participant who completes at least 21 days post conversion and then terminates the XYWAV treatment early. For example, a participant changes dose and/or regimen after 1 week (7 days) post conversion and terminates from the study at Day 38, but remains on stable dose and regimen from Day 24 to Day 37.

Summary of dose and regimen changes will be based on XYWAV Safety analysis set per below:

The time to achieve optimized dose and regimen will be summarized with number of participants, mean, SD, median, minimum, maximum.

The number of changes in dose and regimen from first XYWAV dose to achieve optimized dose and regimen will be summarized with mean, SD, median, minimum, maximum.

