2.1. Study Rationale

Study JZP258-401 is an open-label, single arm, phase 4 interventional trial designed to provide descriptive evidence on the safety, tolerability, effectiveness and optimization of treatment associated with the switching of Xyrem-stable participants with narcolepsy to XYWAV.

The objectives of the study are to delineate the overall clinical experience associated with treatment switching from Xyrem to XYWAV, and evaluate if conversion to XYWAV can be performed with relative ease and rapidity, and with minimal adjustment of dose and regimen. Additionally, the study will collect evidence on whether in comparison with Xyrem, XYWAV offers greater flexibility in dosing with regard to food and improved tolerability for nausea. This study will also evaluate patient preference for the low-sodium formulation of XYWAV relative to that of Xyrem.

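### SAP 9.1.4 narrows the definition of optimized dose without saying so, so two key endpoints would describe only the participants who meet it

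*SAP*

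**What the plan says.** Protocol 9.4.2 defines the endpoint by the last dose: "the optimized dose and regimen indicates the final dose and regimen that remains unchanged throughout the remainder of the Intervention" period. It sets no Visit 7 cut-off and no minimum duration. The lead sentence of SAP 9.1.4 agrees: "the optimized dose and regimen is the final dose and regimen that remains unchanged throughout the remainder of the intervention period".

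SAP 9.1.4 then introduces two bullets as the definition.

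- Completers: "The final dose and regimen that a participant takes before or at Visit 7 that remains unchanged to Visit 8 when the participant completes" treatment, whatever the interval between Visits 7 and 8.
- Early terminators: at least 14 days on the final dose, "for a participant who completes at least 21 days post conversion and then terminates the XYWAV treatment early". The example is a participant who "terminates from the study at Day 38, but remains on stable dose and regimen from Day 24 to Day 37".

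Both dose summaries are assigned to the XYWAV Safety set. Time is summarized with the number of participants, mean, SD, median, minimum and maximum. For the second endpoint the text is "The number of changes in dose and regimen from first XYWAV dose to achieve optimized dose and regimen will be summarized with mean", followed by the SD, median, minimum and maximum; the number of participants is not listed there.

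Four other places bear on this:

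- SAP 9.1.7 splits cataplexy, ESS and PGIc by whether an optimized dose was achieved.
- SAP 7.2.4 allows imputation only for diary, NVAS and ESS data.
- SAP 7.6 lists changes to the analysis sets and the CTCAE reference, and nothing on this definition.
- Footnote 2 of the protocol's schedule makes two final weeks on an optimized dose a requirement, while protocol 4.1 makes it a goal.

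**The concern.** The two definitions cover different people. Under the lead sentence every completer has an optimized dose, and on its natural reading so does every treated participant with dosing data. Under the bullets some do not, and SAP 9.1.4 gives no value, censoring rule or count for them. With no imputation, they simply drop out of both summaries. Whether a participant contributes a value then depends on when the dose last changed, which is the outcome being described.

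This touches the study's main message. Protocol section 2 says "Success in this study will be indicated by seamless switching of the majority of participants from Xyrem to XYWAV, with little or no changes", meaning changes to the dose or regimen, and protocol 2.1 sets out to "evaluate if conversion to XYWAV can be performed with relative ease and rapidity, and with minimal adjustment of dose and regimen". A summary confined to achievers answers these for achievers, not for the participants who switched. The planned statistics for number of changes also give no count of participants with no change or one change, whichever definition applies. The same status sets the 9.1.7 subgroups, so the ambiguity reaches cataplexy, ESS and PGIc.

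**Working it through.** **Inputs.** Conversion is on Day 15 (SAP 7.2.2). Visit 7 is on Day 43 and Visit 8 on Day 57 (target days, SAP 7.2.3). The visit window is +3 days (protocol 1.3). Time is counted as a difference of days; SAP 9.1.4 does not say whether to add one.

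**The SAP's own example.** Day 24 to Day 37 is 37 − 24 + 1 = 14 stable days. Day 38 is 38 − 15 = 23 days post conversion. Both conditions are met, and the time is 24 − 15 = 9 days. The example reproduces.

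**Range of times under each definition, at target days.**

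- Completers under the bullet: at most 43 − 15 = 28 days, or 46 − 15 = 31 if Visit 7 is three days late.
- Completers under the lead sentence: up to 56 − 15 = 41 days (last dosing night Day 56). Those omitted by the bullet have 44 − 15 = 29 to 41 days.
- Early terminators stopping L days post conversion, under the bullet: at most L − 14, which is 7 days at L = 21 and 27 at L = 41. The earliest qualifying stop is Day 15 + 21 = Day 36.

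**Who loses a value.** One example for each group:

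| Participant | Lead sentence | Bullets |
|---|---|---|
| Completer, changes on Days 29 and 50 | 35 days, 2 changes | none (after Visit 7) |
| Stops Day 30, no change | 0 days, 0 changes | none (30 − 15 = 15 < 21) |
| Stops Day 40, changed Day 30 | 15 days, 1 change | none (Days 30 to 39 = 10 < 14) |

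**Direction.** The documents give no late-change or dropout rate, so what follows is illustration only. Assume an achiever mean of 10 days and a non-achiever share of 10%.

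- If all non-achievers are late changers at 35 days, the all-participant mean is 0.9 × 10 + 0.1 × 35 = 12.5 days, and the achiever mean is too short.
- If all are early leavers with no change, it is 0.9 × 10 + 0.1 × 0 = 9.0 days, and the achiever mean is too long.
- For shares from 2% to 20% the two cases run from 10.5 to 15.0 and from 9.8 to 8.0 days.

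Number of changes is no clearer. Late changers have at least one change. So do terminators at 21 days or later with under 14 stable days, because with no change they would have at least 21. Leavers before 21 days may have none.

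**What a median would show.** This is a bound under assumed counts. With 100 treated and all having a value, a median of 0 changes guarantees 51 participants with none (the 50th and 51st values must both be 0). If 10 have no value, n = 90 and the guarantee is 46 of the 100 treated, which is not a majority.

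**The case against.** The strongest reply is that the bullets are the technical detail that protocol 9.4 says the SAP will supply. They have support in footnote 2 and protocol 4.1, and 9.1.7 plainly expects non-achievers, so there is little doubt which text governs. This stands in part. It makes the bullets the likelier reading, but it does not remove the conflict with protocol 9.4.2 or the silence of 9.1.4 and 7.6. Nor do the bullets match footnote 2: with Visit 7 three days late and Visit 8 on target, 57 − 46 = 11 days is enough.

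A reader might infer that the reported mean time must be too short. The documents do not support that. The summary pools completers with early terminators, and omitting early leavers who never changed pushes the mean the other way. Even among completers, the strict ordering holds only at target days: one kept with Visit 7 on Day 46 may have 31 days, while one omitted after changing on Day 44 has 29.

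A reader might also infer that late-changing completers cannot be identified at all. That goes too far. The time summary gives n, and SAP 7.1 asks for n with continuous variables generally. SAP 9.1 plans effectiveness tables in both the XYWAV Safety and XYWAV Efficacy sets. The Efficacy set is limited to those who finish the study, so non-achievers in its 9.1.7 tables are the completers who changed late, apart from missing questionnaires. The shortfall can therefore be partly worked out, but no planned dose table reports it.

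Finally, the success sentence is introductory prose and not an endpoint, and the last two weeks are expected to be stable (protocol 4.2). Both are fair. They make the table of change counts supplementary, and they leave the frequency of late changes unknown.

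**Conclusion.** The point holds as a matter of definition and reporting. If the bullets govern, as the wording and 9.1.7 suggest, time to optimized dose and number of changes describe achievers only. Three groups are left out of summaries that are nominally on the XYWAV Safety set, and neither 9.1.4 nor 7.6 says so.

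The size and direction of any bias in the pooled summaries cannot be determined from the documents. The only figures fixed by the schedule are the limits at target visit days (28 days for completers kept, 29 to 41 for late changers omitted), and these blur by up to three days with the visit window. The study is descriptive with no hypothesis tests, so nothing inferential fails. What is at risk is that figures for achievers are read as figures for everyone who switched. The correction is worth making before the analysis because it is cheap.

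**What to change.** Reconcile the lead sentence, the bullets, protocol 9.4.2, protocol 4.1 and footnote 2 of the schedule into one stated analysis definition, and list it in SAP 7.6. This concerns the analysis definition only and proposes no dosing rule.

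- If the bullets are kept: beside the time summary, report the number and percent of all XYWAV Safety participants who did and did not meet the definition. Split those who did not into change after Visit 7, left before 21 days, and under 14 stable days. Label the summary as covering achievers only.
- If the lead sentence is kept: revise the 9.1.7 split, which would then have no non-achievers among completers.
- In either case: add a supplementary table of the number of dose or regimen changes (0, 1, 2, 3 or more) over the intervention period for all treated participants. It is supplementary because the endpoint itself counts changes only up to the optimized dose.

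The cost is SAP wording, one entry in 7.6 and a few tables. Protocol 6.4 already has dose and regimen adjustments recorded in the eCRF, so no new data are needed. The reported figures may be less favourable.
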